#### 9.3.1 Inclusion criteria

Subjects who meet all the following criteria are eligible to participate in this clinical trial.

- (1) Crohn's disease patients aged 18 or over and under 65 on the date of consent.
- (2) Patients diagnosed on basis of clinical findings, endoscopic findings, etc. with small intestine-type, small and large-intestine type, or large-intestine type Crohn's disease at least 12 weeks before giving consent.
- (3) Patients with a baseline (at Week 0 before the start of IMP administration) disease severity ranging from moderate to severe. CDAI score between 220 and 450, and a PRO2 score between 14 and 34.
- (4) Patients with a Simple Endoscopic Score for Crohn's Disease (SES-CD) ≥7 (or for patients with isolated ileal disease, ≥4 in ileum segment) in the screening period, with one or more ulcers (in SES-CD score, ulcer presence subscore ≥ 1 in any segment) assessed by colonoscopy and confirmed by a centralised review.
- (5) Patients who received adrenocorticosteroids or immunomodulators in the past, but showed no therapeutic response (insufficient response) or the drugs were not tolerated (intolerance). Alternatively, patients who cannot taper adrenocorticosteroids (dependence). Alternatively, patients who showed no therapeutic response after administering biologic(s) (primary nonresponse), patients who initially showed therapeutic response but it lessened or disappeared afterwards (secondary nonresponse), or patients who did not tolerate the drug (intolerance). (Detailed criteria are described in Attachment 7 and Attachment 8).
- (6) If the patients are taking 1,200 kcal/day or less enteral nutrition, the dosage and administration have not changed for at least 4 weeks prior to the start of the IMP administration.
- (7) If the patients are taking aminosalicylic acid (5-ASA), salazosulfapyridine, or antibiotics for the treatment of Crohn's disease (metronidazole, ciprofloxacin, etc.), the dosage and administration have not changed for at least 4 weeks prior to the start of the IMP administration.
- (8) If the patients are taking under 30 mg/day of oral prednisolone (or equivalent adrenocorticosteroid) or 9 mg/day or less of oral budesonide, the dosage and administration have not changed for at least 4 weeks prior to the start of the IMP administration.

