Attachment 6 shows a detailed list of prohibited concomitant drugs.

# 9.4.7.1.2 Restricted concomitant drugs

The following drugs may be used in combination with the IMP, but the dosage and administration may not be changed until Week 12 (or until discontinuation).

In principle, the dosage and administration may not be changed from Week 12 until the end of the extension period, but dosage reduction, discontinuation, increasing dosage after dosage reduction (up to the dosage used at the start of the IMP administration) or resuming administration after discontinuation is allowed. If the symptoms of subjects taking oral adrenocorticosteroids or receiving oral budesonide improve (CR100 achievement), the dosage is to be reduced in principle, using as reference the steroid dosage reduction schedule set forth in Attachment 9.

- Aminosalicylic acid (5-ASA)
- Salazosulfapyridine
- Antibiotic drugs for the treatment of Crohn's disease
- Oral administration of adrenocorticosteroids (less than 30 mg/day of prednisolone equivalent), oral budesonide (9 mg/day or less)
- Azathioprine (AZP)
- Mercaptopurine (6-MP)
- Methotrexate (MTX)
- Enteral nutrient preparation (1,200 kcal/day or less)

The SARS-CoV-2 vaccine may be used concomitantly, but it should not be administered within 7 days before or after the IMP administration.

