#### 9.5.1.3.3 Evaluation of corticosteroid dose reduction

Steroid dose is to be reduced, in principle, using as reference the steroid dose reduction schedule outlined in Attachment 9 in subjects who are on concomintant adrenocorticosteroids (including concomintant budesonide) and achieve CR100 response.

Steroid-free remission is defined as clinical remission (CDAI remission or PRO2-remission) in subjects who have become steroid free through steroid reduction. Similarly, steroid-free clinical response is defined as clinical response (CR70 response, CR100 response, PRO2-CR5 response and PRO2-CR8 response) in subjects who have become steroid free through steroid reduction.

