4.5.2 Secondary Endpoints for Efficacy

- CR70 response rate, CR100 response rate (excluding Week 12) and CDAI remission rate (proportion of subjects with below 150 points) at each evaluation time
- Proportion of subjects with at least 5-point reduction in PRO2 from baseline (PRO2-CR5 response rate), proportion of subjects with at least 8-point reduction from baseline (PRO2-CR8 response rate), and proportion of subjects with below 8 points (PRO2-remission rate) at each evaluation time
- Proportion of subjects with at least 50% improvement in SES-CD score from prior to IMP administration (endoscopic response rate) and proportion of subjects with 2 or less in SES-CD score (endoscopic remission rate) at Week 12
- Change and percent change in CDAI score from baseline at each evaluation time
- Change and percent change in PRO2 from baseline at each evaluation time
- Change and percent change in SES-CD score from baseline at Week 12
- In subjects who were concomitantly taking adrenocorticosteroid at remission induction period, proportion of subjects who achieved steroid-free maintenance (steroid-free remission rate, steroid-free improvement rate) through steroid dose reduction and clinical remission (CDAI remission or PRO2 remission) or clinical improvement (CR70 response, CR100 response, PRO2-CR5 response or PRO2-CR8 response)
- In subjects who were concomitantly taking adrenocorticosteroid at remission induction period, dosage (mg/day), change and percent change of adrenocorticosteroid from baseline.

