The dose at baseline is calculated as the sum of doses in mg/day of all adrenocorticosteroids that are taken the baseline day. Doses at every visit are calculated as the sum of all adrenocorticosteroids taken from previous time point to the current visit date, for example, dose at week 2 is the sum of all doses taken from baseline to week 2 date.

Adrenocorticosteroids related to Crohn's disease will be identified as any concomitant corticosteroid at remission induction period in the database that has reported in the eCRF an indication to primary disease (Crohn's disease). Steroid free patients will be identified as patients that are taking any adrenocorticosteroid related to Crohn's disease at baseline and they stop taking them before week 12.

Subjects with missing secondary endpoint data due to premature discontinuation before 12 weeks after administration, or other reasons are treated as non-responders (NRI) in the modeling of the endpoints.

Secondary analysis will be performed in the FAS population and in the PPS population.

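### The steroid-dose endpoint adds raw milligrams of different corticosteroids, so pooled dose and absolute change by arm depend on which steroid the patients take (minor; descriptive secondary endpoint)

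*SAP*

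**What the plan says.** SAP 4.5.2 lists as a secondary endpoint, in subjects on concomitant corticosteroids, "dosage (mg/day), change and percent change of adrenocorticosteroid from baseline". SAP 6.8.2 says how the dose is formed. At baseline, "The dose at baseline is calculated as the sum of doses in mg/day of all adrenocorticosteroids that are taken the baseline day". After baseline, "Doses at every visit are calculated as the sum of all adrenocorticosteroids taken from previous time point to the current visit date". The drugs that enter the sum are "any concomitant corticosteroid at remission induction period in the database that has reported in the eCRF an indication to primary disease", so the total is not confined to one molecule. The SAP gives no equivalence factor, no conversion table and no separate budesonide summary.

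Where the protocol has to express an amount of steroid, it uses two scales:

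- Section 9.3.1 admits patients taking "under 30 mg/day of oral prednisolone (or equivalent adrenocorticosteroid) or 9 mg/day or less of oral budesonide".
- Section 9.4.7.1.2 repeats the split for concomitant use: "Oral administration of adrenocorticosteroids (less than 30 mg/day of prednisolone equivalent), oral budesonide (9 mg/day or less".
- Section 9.5.1.3.3 applies the dose-reduction evaluation to subjects on "concomintant adrenocorticosteroids (including concomintant budesonide) and achieve CR100 response", so budesonide belongs to the quantity being evaluated.

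The protocol's own endpoint wording (9.7.1.1.2 and 9.7.1.6.2) names no unit for steroid dose.

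**The concern.** A total in milligrams means something only if a milligram of each component means the same thing. The protocol's two scales show that the sponsor does not treat corticosteroids as interchangeable by weight, yet the SAP adds them one for one.

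At stake is the comparison of arms on steroid dose. Protocol 9.7.2 puts enrolment at 25 subjects. Steroid users are a subset of these, and SAP 6.1 and 10 split the tables further into Japanese and non-Japanese. In groups that small, a difference between arms in mean dose or mean change could reflect which steroid the patients were on and not how much they reduced it. The fault is in the unit. It is distinct from the fault in time basis in the same paragraph of the SAP, where one day's dose is compared with an interval total, and correcting that one would leave the unit as it is.

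**Working it through.** The plan states no figure for this endpoint, so there is nothing to reproduce. The check applies the SAP's summing rule to regimens within the protocol's limits, using mg/day at both times so that the time-basis fault does not interfere.

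**Inputs.** Raw summing rule: SAP 6.8.2. Limits of under 30 mg/day prednisolone equivalent and at most 9 mg/day budesonide: Protocol 9.3.1 and 9.4.7.1.2. The documents give no conversion factor. Let k be prednisolone-equivalent mg per mg of budesonide, an assumption shown over k = 1 to 5. The ratio of the two limits, 30/9 = 3.33, is used only as a midpoint; the protocol does not state it as an equivalence.

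**Formulas.** With P mg/day of prednisolone and B mg/day of budesonide, the SAP's dose is P + B. A common-scale dose would be P + kB. The two agree only at k = 1.

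**1. Absolute change, one subject (no k needed).** Budesonide 9 to 0: 0 - 9 = -9 mg. Prednisolone 29 to 20: 20 - 29 = -9 mg. Stopping budesonide from its ceiling and cutting prednisolone by 9/29 = 31% receive the same score.

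**2. Pooled mean and drug mix (no k needed; mix assumed).** Four users all stop their steroid.
- All on prednisolone 20: baseline mean 20; mean change 4 x (-20)/4 = -20 mg.
- Two on prednisolone 20 and two on budesonide 9: baseline mean (20 + 20 + 9 + 9)/4 = 14.5; mean change (2 x (-20) + 2 x (-9))/4 = -14.5 mg.

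Every user stops in both groups. The gap of 20 - 14.5 = 5.5 mg, at baseline and in change, comes from the drug mix alone.

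**3. Pooled change with partial reduction (k needed).** Half go from prednisolone 20 to 10 and half from budesonide 9 to 3. With two subjects each, the mean change is (2 x (-10) + 2 x (-6k))/4. The raw sum (k = 1) gives -8 mg; k = 2 gives -11, k = 3.33 gives -15 and k = 5 gives -20.

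**4. Percent change in a two-drug subject (k needed).** Baseline is prednisolone 20 plus budesonide 9, a raw dose of 29.

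| | Raw | k = 2 | k = 3.33 | k = 5 |
|---|---|---|---|---|
| Common-scale baseline, 20 + 9k | 29 | 38 | 50 | 65 |
| Budesonide stopped, -9k/(20 + 9k) | -31% | -47% | -60% | -69% |
| Prednisolone stopped, -20/(20 + 9k) | -69% | -53% | -40% | -31% |

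The raw rule understates one reduction and overstates the other.

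**5. Percent change in a single-drug subject.** Budesonide 9 to 6: k(6 - 9)/(9k) = -33.3% for every k. The factor cancels, so this measure is not affected.

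**6. When it matters.** Protocol 9.4.7.1.2 holds the dose of these drugs fixed until Week 12, and the time points named in SAP 6.8.2(f) are baseline and Weeks 2, 4, 8 and 12. On a daily basis, a compliant subject therefore has zero change in any unit over that window; what remains is the pooled dose level and any deviations. After Week 12, Protocol 9.4.7.1.2 allows reduction and stopping. SAP 6.8 and Protocol 9.7.1.10 extend the efficacy analysis to the entire administration period, and there absolute change is exposed.

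**The case against.** The strongest reply is that the protocol uses prednisolone equivalents for eligibility and concomitant-drug limits, not to define the endpoint, so the SAP breaks no endpoint rule. That stands: this is a defect in the SAP's own definition, judged against the scales the protocol uses elsewhere. It is still more than missing detail, because the SAP states a rule, and the rule gives drug-dependent pooled figures when followed exactly.

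It also stands that the size in this trial cannot be fixed. The documents give no conversion factor and no count of steroid, budesonide or two-drug users. The steroid dose-reduction schedule (Attachment 9) and the drug list (Attachment 6) are not in the supplied text, and nothing says whether the database holds converted doses. If it does, the SAP should say so.

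A reader might go further and infer three things that the documents do not support:

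- **That switches between steroids will be misreported.** Doses are fixed to Week 12, and substitution is not among the later changes that Protocol 9.4.7.1.2 lists. Whether such a switch would be scored in the wrong direction also depends on the factor that is not given.
- **That baseline, change and percent change are all distorted alike.** Step 5 shows that percent change in single-drug users is not.
- **That this endpoint is the main evidence of steroid sparing.** Steroid-free remission and response are separate listed endpoints (SAP 4.5.2; 6.8.2 d and e). They depend on stopping, not on milligrams, and are unaffected.

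**Conclusion.** The point holds as a minor correction to a descriptive secondary endpoint. As written, pooled baseline dose, pooled absolute change, and percent change in any subject on two steroids depend on which drugs are taken. That the pooled figures depend on drug mix needs no outside factor: a 5.5 mg gap appears in the four-user illustration with no difference in outcome. Only the size of the distortion on a common scale depends on the assumed k. The four-user mix and the two-drug subject are illustrations; the documents do not show that such patients were enrolled.

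The practical effect is confined to dose levels up to Week 12 and to dose change in the entire-administration-period analysis. The primary analysis and its decision rule are not touched.

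**What to change.** In SAP 6.8.2 and 4.5.2:

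- Convert each systemic corticosteroid to prednisolone-equivalent mg/day with one conversion table, fixed before the database lock for the period concerned, and then sum.
- Summarise oral budesonide separately in mg/day, in line with Protocol 9.3.1 and 9.4.7.1.2.
- Compute change and percent change within each scale. List any subject who moves between scales, since percent change from a zero baseline on the new scale is undefined.
- If the database already holds converted doses, state that and cite the table used.

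Make the edit together with the separate correction of the time basis, so that baseline and visits are both expressed per day.

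The cost is a few lines of SAP text, a lookup table in programming and one more summary row, with fewer patients per row. Drug name and amount are already recorded under Protocol 9.4.7, so no new data are needed and patient management does not change.

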6.8 Efficacy Analysis

Efficacy analysis will be based in the FAS and PPS populations. Primary analysis will be produced in the FAS population. Primary analysis will be repeated in the PPS population as a sensitivity analysis.

Efficacy analysis will be done for the remission-induction period and the entire administration period.

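### SAP 6.8.2 compares a steroid total over an interval with a daily baseline dose, and its only steroid-free rule requires stopping while the protocol still fixes the dose

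*SAP*

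**What the plan says.** **Dose.** For baseline, SAP 6.8.2 states: "The dose at baseline is calculated as the sum of doses in mg/day of all adrenocorticosteroids that are taken the baseline day". For later visits: "Doses at every visit are calculated as the sum of all adrenocorticosteroids taken from previous time point to the current visit date". Its worked example is that "dose at week 2 is the sum of all doses taken from baseline to week 2 date". Item f of the same section reports change and percent change at Weeks 2, 4, 8 and 12. SAP 4.5.2 names the endpoint as "dosage (mg/day), change and percent change of adrenocorticosteroid from baseline".

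**Steroid-free status.** SAP 6.8.2 identifies these patients as those on a Crohn's-related steroid "at baseline and they stop taking them before week 12". The Crohn's-related steroids are found among "any concomitant corticosteroid at remission induction period in the database" whose recorded indication is the primary disease. Items d and e describe steroid-free rates at Weeks 2, 4, 8 and 12.

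**What surrounds these rules.** For the restricted drugs, which include oral steroids and oral budesonide, Protocol 9.4.7.1.2 says that "the dosage and administration may not be changed until Week 12 (or until discontinuation"). From Week 12 to the end of the extension it permits reduction and stopping. Protocol 9.5.1.3.3 defines steroid-free remission and response in subjects who become steroid free through dose reduction, and sets no Week 12 limit. Protocol 9.7.1.6.2 asks for steroid-free rates at each evaluation time. SAP 6.8 adds: "Efficacy analysis will be done for the remission-induction period and the entire administration period". Protocol 9.7.1.10 likewise repeats the efficacy analyses for the whole dosing period. SAP 6.11 declares no modification from the protocol.

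**The concern.** The dose table would subtract a rate from an amount. Its values would then depend mainly on how many days lie between time points, and a patient on a constant or falling dose could appear to have a large increase. Steroids are also added together with no stated equivalence, although Protocol 9.4.7.1.2 uses prednisolone equivalents and gives budesonide its own limit.

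The steroid-free rule has a different fault: it looks for stopping in the one period when the protocol bars any change. Up to Week 12 it can register only protocol deviations. After Week 12, when tapering is allowed, the SAP gives no rule of its own. Protocol 9.5.3 includes steroid-free remission and response on the strength of regulatory guidance, and as written the SAP cannot deliver them in a usable form.

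**Working it through.** The documents give no figure to reproduce, so the SAP rule is applied to simple cases.

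**Inputs**
- Baseline value: D mg/day (SAP 6.8.2).
- Visit value, literal reading: total taken over the n days since the previous time point (SAP 6.8.2).
- Interval lengths: the reporting times 0, 2, 4, 8 and 12 weeks give n = 14, 14, 28 and 28 days.
- Visit window: ±3 days from Week 2 to Week 12 (Protocol 9.5.2.1).
- Doses of 20 and 15 mg/day are illustrative assumptions. The constant-dose percentages do not depend on them.

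**1. Constant dose, interval total.** Percent change = 100 × (D × n − D) / D = 100 × (n − 1). The true value is 0%.
- n = 14: 100 × 13 = +1300% (at 20 mg/day, 280 against 20).
- n = 28: 100 × 27 = +2700% (560 against 20).
- The step between Weeks 4 and 8 comes only from the longer interval.
- If the previous time point for Weeks 8 and 12 is the preceding visit (Week 6 or 10), n = 14 and the value is +1300%.
- Window at Week 2: n = 11 gives +1000%; n = 17 gives +1600%.
- Counting both end days makes n = 15 or 29, hence +1400% or +2800%.

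**2. True 50% reduction over the whole interval, interval total.** Percent change = 100 × (0.5n − 1).
- n = 14: +600%. n = 28: +1300%.
- The formula shows no change only after a reduction of 1 − 1/n: 92.9% at 14 days, 96.4% at 28 days.

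**3. Alternative reading: add the mg/day of each steroid record in the interval.** The two readings compare as follows for a 20 mg/day baseline.

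| Case | Interval total | Record sum | True change in daily dose at visit |
|---|---|---|---|
| Constant, one record, 14 days | 280: +1300% | 20: 0% | 0% |
| 20 reduced to 15 within the interval | depends on the day of change | 20 + 15 = 35: +75% | (15 − 20)/20 = −25% |
| Stopped halfway through 28 days | 20 × 14 = 280: +1300% | 20: 0% | −100% |

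The record sum is right for a single constant record and wrong in both cases where the dose changes.

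**4. Daily scale.** Interval total divided by n returns D for a constant dose (0%) and 0.5D for a 50% reduction held throughout (−50%). Both are correct.

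**5. Steroid-free rule, by timing**
- Stop before Week 12: meets the SAP rule, but for a continuing patient it departs from Protocol 9.4.7.1.2.
- Stop after Week 12: permitted by Protocol 9.4.7.1.2 and within the definition in Protocol 9.5.1.3.3, but never meets the SAP rule.

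The expected steroid-free count among compliant continuing patients is therefore 0 in both arms at Weeks 2, 4, 8 and 12.

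**The case against.** The strongest reply on the dose is that SAP 4.5.2 fixes the unit as mg/day and the baseline sentence uses it, so the visit sentence may simply continue the same quantity across steroid records. A compliant patient with one record then scores 0% at every time point that SAP 6.8.2 lists, because the dose is fixed to Week 12. That is fair: the +1300% and +2700% figures hold only on the literal reading. The record-sum reading still fails when a dose changes, which is what the endpoint is meant to measure and what the protocol allows in the later period. It also sits poorly with the SAP's own example of accumulating doses from baseline to Week 2. That example skips the Week 1 visit, so it does favour reporting times as the meaning of previous time point; the text should still say so.

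On steroid-free status, part of the conflict starts in the protocol. Section 9.7.1.6.2 asks for rates at each evaluation time while section 9.4.7.1.2 fixes the dose to Week 12, so the early tables would be uninformative even without the SAP cut-off. That stands. The cut-off itself is a SAP addition.

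It can also be said that all items in SAP 6.8.2 stop at Week 12, that nothing states the flag will be carried forward, and that Protocol 9.7 lets the plan be fixed before each database lock. The later loss is indeed conditional. The alternative, however, is that the SAP has no operational rule for that period.

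Finally, these are descriptive tables in the steroid-taking part of 25 enrolled subjects (Protocol 9.7.2), and no efficacy decision rests on them. That limits the weight of the point but does not remove it.

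**Conclusion.** The concern holds on both counts and should be fixed. The visit-dose rule does not give a valid change in mg/day under either reading: the literal one inflates an unchanged dose by (n − 1) × 100%, and the lenient one fails whenever a dose changes. The steroid-free rule cannot be met by a compliant continuing patient by Week 12. If applied to the entire administration period, it excludes everyone who tapers when permitted.

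The percentages assume the literal reading and nominal intervals. The later loss assumes that the cut-off, or the restriction to steroids of the induction period, is carried forward. Attachment 9, which holds the taper schedule, is not among the documents reviewed, and Protocol 9.5.1.3.3 ties reduction to CR100 without saying when. After Week 12 all continuing patients receive open-label E6011, so later rates are descriptive under any definition. The primary CR100 analysis is not affected.

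**What to change.** 1. Derive the dose at each visit in mg/day, either as the daily dose on the visit date (the baseline rule) or as the interval total divided by the days in the interval. Name one, because they differ when a dose changes: a stop halfway through 28 days from 20 mg/day gives 0 on the visit date but 280/28 = 10 as an interval mean. If an interval is used, define the previous time point.
2. State one steroid-equivalence scale for adding different steroids.
3. Replace the single flag with a status at each visit: on a Crohn's-related steroid at baseline, and steroid free through reduction at that visit, in line with Protocol 9.5.1.3.3.
4. Apply that status at the scheduled CDAI/PRO2 visits after Week 12 in the entire-administration-period analysis, and identify Crohn's-related steroids over that period too.
5. Keep the Week 2 to 12 tables that Protocol 9.7.1.6.2 requires, with a note that the fixed dosage makes them uninformative.
6. Reconcile Protocol 9.4.7.1.2, 9.5.1.3.3 and 9.7.1.6.2 with SAP 6.8.2. No clinical rule is proposed here. List any remaining departure in SAP 6.11.

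The cost is SAP wording and two derivations. Protocol 9.4.7 already has the administered amount and the start and end dates recorded for all drugs, so no new data are needed.

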#### 9.7.1.6.2 Analysis of secondary efficacy endpoints

- CDAI response rate [CR70, CR100 (excluding Week 12)] and remission rate are to be calculated by treatment group and evaluation time. Summary statistics for CDAI value, change and percent change from baseline are also to be calculated by treatment group and evaluation time.
- PRO2 response rate (PRO2-CR5, PRO2-CR8) and remission rate are to be calculated by treatment group and evaluation time. Summary statistics for PRO2 value, change and percent change from baseline are also to be calculated by treatment group and evaluation time.
- SES-CD endoscopic response rate and endoscopic remission rate are to be calculated by treatment group and evaluation time. Summary statistics for SES-CD value, change and percent change from baseline are also to be calculated by treatment group and evaluation time.
- Steroid-free remission rate and steroid-free response rate in subjects concomitantly using adrenocorticosteroids is to be tabulated by treatment group and evaluation time. Summary statistics for steroid dosage, change and percent change from baseline are also to be calculated for each treatment group and evaluation time.

Subjects with missing secondary endpoint data due to premature discontinuation before 12 weeks after administration or other reasons are treated as non-responders (NRI) in the analysis of secondary endpoints.

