6.8.2 Secondary Efficacy analysis

- a. CDAI response rate (CR70) and remission rate at week 12 will be analyzed using logistic regression model considering randomization strata (Japanese/Non-Japanese and Male/Female) and treatment group as fixed factor. This model will estimate the Odds Ratio between the treatment arms.

Also, the CDAI response rate (CR70, CR100) and remission rate are also to be described by treatment group week 2, week 4, week 8 and week 12.

And finally, CDAI, change and percentage change from baseline will be descriptively analyzed too by treatment group at baseline, week 2, week 4, week 8 and week 12.

- b. PRO2 response rate (PRO2-CR5, PRO2-CR8) and remission rate at week 12 will be analyzed using logistic regression model considering randomization strata (Japanese/Non-Japanese and Male/Female) and treatment group as fixed factor. This model will estimate the Odds Ratio between the treatment arms.

Also, the PRO2 response rate (PRO2-CR5, PRO2-CR8) and remission rate are also to be described by treatment group week 2, week 4, week 8 and week 12.

And finally, PRO2, change and percentage change from baseline will be descriptively analyzed too by treatment group at baseline, week 2, week 4, week 8 and week 12.

- c. SES-CD endoscopic response rate and endoscopic remission rate at week 12 will be analyzed using logistic regression model considering randomization strata (Japanese/Non-Japanese and Male/Female) and treatment group as fixed factor.
Also, the SES-CD endoscopic response rate and remission rate are also to be described by treatment group week 2, week 4, week 8 and week 12.
And finally, SES-CD endoscopic, change and percentage change from baseline will be descriptively analyzed too by treatment group at baseline, week 2, week 4, week 8 and week 12.
- d. Steroid-free CDAI response rate (CR70, CR100) and remission rate will be described by treatment group at week 2, week 4, week 8 and week 12.
- e. Steroid-free PRO2 response rate (PRO2-CR5, PRO2-CR8) and remission rate will be described by treatment group at week 2, week 4, week 8 and week 12.
- f. The dose of adrenocorticosteroids related to Crohn's disease will be described using the change and percentage change from baseline by treatment group at baseline, week 2, week 4, week 8 and week 12.

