10 GENERAL FORMAT OF TABLES, FIGURES AND SUBJECT DATA

Tables and listings will be produced in accordance with the principles outlined by the ICH E3 guideline. All summary tables will be presented by treatment group and race (all, Japanese and non-Japanese).

The design of the tables will be clear and concise so that comparative reading is easily possible.

All descriptive variables will be tabulated. Quantitative variables will be described showing their number of available and missing observations, mean and its CI (95% level), median, standard deviation, the range (minimum and maximum) and the first and third quartiles. Frequency and percentage will describe qualitative variables.

Missing values will be tabulated with their frequency but will not be included in the calculation of percentages. Analysis will be based on observed cases, i.e., no replacement of missing data is planned in general except otherwise planned in the appropriate statistical methodology section (section 11, section 12 or 14).

Pharmacokinetic data (E6011 serum concentrations) will be summarized by treatment group and race (All, Japanese and Non-Japanese) and evaluation time, including the number of sample results, minimum, medium, maximum, mean, standard deviation and coefficient of variation (CV). In addition, geometric means and geometric CV will be also shown.

Serum E6011 concentration vs time curves will be prepared. A serum concentration profile will be prepared for each subject and shown individually on a single plot per patient. A plot showing all serum profiles generated per treatment group will be prepared.

Summary serum E6011 concentration vs time profiles will also be prepared. A geometric mean serum profile will be shown by treatment group individually and grouped by treatment.

Pharmacodynamic data (serum total FKN concentrations, faecal calprotectin and serum CRP concentration measured values, change and % change from baseline) will be summarized by treatment group, evaluation time and race (all, Japanese and non-Japanese), including the number of sample results, minimum, medium, maximum, mean, standard deviation and coefficient of variation (CV). In addition, geometric means and geometric CV will be also shown.

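### SAP 6.8.2 limits non-responder imputation to the modelling, so the described secondary response rates default to observed cases, which departs from the protocol

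*SAP*

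**What the plan says.** **Protocol 9.7.1.6.2.** For CDAI and for PRO2, response rate and "remission rate are to be calculated by treatment group and evaluation time". The endoscopic and steroid-free rates are handled the same way, and no model is named. Subjects whose secondary data are missing, through dropout before 12 weeks or for other reasons, "are treated as non-responders (NRI) in the analysis of secondary endpoints".

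**SAP 6.8.2.** The SAP adds a model: "CDAI response rate (CR70) and remission rate at week 12 will be analyzed using logistic regression model", with parallel items for PRO2 and SES-CD. As a separate task, "the CDAI response rate (CR70, CR100) and remission rate are also to be described by treatment group week 2, week 4", with Weeks 8 and 12 following. Steroid-free rates are described only and never modelled. The closing sentence on missing data says that the affected subjects "are treated as non-responders (NRI) in the modeling of the endpoints".

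**SAP 10.** The general rule for tables is: "Missing values will be tabulated with their frequency but will not be included in the calculation of percentages". It adds that "no replacement of missing data is planned in general except otherwise planned in the appropriate statistical methodology section", and points to sections 11, 12 or 14.

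**SAP 6.11** states that nothing was modified from the protocol's statistical section.

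**The concern.** In the protocol, the non-responder rule can only govern the tabulated rates, because the protocol plans nothing else for these endpoints. The SAP attaches the rule to the modelling and leaves the tables under an observed-case default. Three consequences follow if a programmer works from the SAP text:

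- Described rates are conditional on having a value at the visit. FAS membership needs only a baseline CDAI and one later CDAI (SAP 5.1), so a subject who leaves early can be in the FAS with Week 12 missing.
- At Week 12 the table and the odds ratio for the same endpoint can rest on different data.
- CDAI and PRO2 rates at Weeks 2, 4 and 8, and all steroid-free rates, are never modelled, so they get no non-responder imputation at all.

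SAP 6.8.3 calls the analysis mainly descriptive, so these tables are a large part of the secondary output.

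**Working it through.** **Step 1. Which rule reaches which output**

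| Output | Protocol 9.7.1.6.2 | SAP as written |
|---|---|---|
| Week 12 logistic models (CR70, CDAI remission, PRO2, SES-CD) | not planned | non-responder imputation (6.8.2) |
| Described CDAI and PRO2 rates, Weeks 2, 4, 8, 12 | non-responder imputation | observed cases (10) |
| Described endoscopic rates, Week 12 | non-responder imputation | observed cases (10) |
| Described steroid-free rates | non-responder imputation | observed cases (10) |
| Described Week 12 CR100 | the primary endpoint, imputed (9.7.1.6.1) | unclear: SAP 1 imputes without restriction; 6.8.1 imputes in the modelling; 6.8.2 describes it |

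SAP 10 gives way where a methodology section plans otherwise, but 6.8.2 plans otherwise only for modelling. The sections that SAP 10 points to do not help: section 11 is the reference list, and the SAP has no section 12 or 14.

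**Step 2. The plan's own figures**

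The documents give no dropout rate and no assumed response rates, so there is no planned figure on this point to reproduce. The one operating figure is the probability above 80% of confirming efficacy with 20 per arm and a true difference of 40 points. It does reproduce: with Jeffreys priors and exact enumeration it is 80.7% to 87.4% for assumed placebo rates of 5% to 60%. It belongs to the primary analysis and does not bear on this point.

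**Step 3. Size of the discrepancy**

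For an arm with n subjects, r responders and k missing:

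- imputed rate = r/n
- observed-case rate = r/(n − k)
- ratio of the two = n/(n − k) = 1/(1 − m), with m = k/n

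The ratio is 1.05 at 5% missing, 1.11 at 10%, 1.25 at 20% and 1.43 at 30%.

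Total enrolment was 25 (Protocol 9.7.2). Everything else here is assumed for illustration: a 13 vs 12 split, 6 responders on E6011, 3 on placebo, and the missing counts.

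- Imputed: 6/13 = 46.2%, 3/12 = 25.0%, difference 21.2 points.

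| Missing, E6011 vs placebo | E6011, observed | Placebo, observed | Difference (points) |
|---|---|---|---|
| 2 vs 2 | 6/11 = 54.5% | 3/10 = 30.0% | 24.5 |
| 3 vs 1 | 6/10 = 60.0% | 3/11 = 27.3% | 32.7 |
| 1 vs 3 | 6/12 = 50.0% | 3/9 = 33.3% | 16.7 |

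With no missing data the two rules agree.

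**The case against.** The best defence is that modelling is used loosely here to mean analysis. SAP 6.8.1 uses nearly the same phrase for the Bayesian primary analysis, so the word is not tied to logistic regression. The sentence in 6.8.2 follows all the listed items and speaks of missing secondary data in general. SAP 10 is a formatting section with a broken pointer. No sentence says outright that secondary rates are observed-case. The tables also show the number missing, so a reader could rebuild the imputed rate.

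Part of this stands: the observed-case result is the most natural reading, not an explicit statement. The loose reading is the weaker one, because SAP 6.1 presents descriptive methods as primary and modelling as an addition, and 6.8.2 keeps the same split between items analysed by a model and items described. Even if the loose reading were intended, two programmers could produce different tables from this text.

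A reader might also infer more than the documents support:

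- **That the primary result is compromised.** It is not. SAP 6.8.1 applies the imputation in the Bayesian analysis, and the SAP synopsis applies it to Week 12 CR100 without restriction. A separately described Week 12 CR100 rate could differ from the primary result; it need not.
- **That endoscopic rates at Weeks 2, 4 and 8 are affected.** SAP 6.8.2 lists those weeks, but in the double-blind period colonoscopy is scheduled only at screening, Week 12 and discontinuation. The point applies to Week 12 only.
- **That observed cases favour E6011, or are biased against an unbiased reference.** Non-responder imputation is a failure convention, and Step 3 shows the difference shrinking as well as growing.

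**Conclusion.** The conflict holds. The protocol imputes non-response in the tabulated secondary rates; the SAP, on its most natural reading, does not, and 6.11 does not declare the change. SAP 6 names protocol version 10 as its basis, whereas the comparison here is with version 11.

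The size depends on missingness that the documents do not give. Each arm's rate rises by 1/(1 − m). With about a dozen patients per arm, a few unevenly distributed missing values can move the between-arm difference by roughly 5 to 12 points in either direction (21.2 to 16.7, or 21.2 to 32.7), under the assumed counts. The primary decision rule does not change. This should be corrected before the tables are produced, but it does not threaten the trial's main conclusion.

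**What to change.** In the missing-data sentence that closes SAP 6.8.2, replace the final phrase so that the imputation applies *in both the modelling and the descriptive summaries of binary secondary efficacy endpoints, at visits through Week 12 where the assessment is scheduled; the denominator is all subjects in the relevant analysis set (FAS or PPS), and for steroid-free endpoints those in that set taking corticosteroids at baseline*. Apply the same wording to the described Week 12 CR100 rate. Keep the LOCF and observed-case sensitivity analyses of 6.8.1, and show observed-case secondary rates only as a labelled supplement. If observed cases are intended, declare the departure in 6.11.

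The limits in that wording are needed. A blanket rule with the FAS as denominator would clash with the PPS analysis and with the steroid-user denominator. It would override the planned sensitivity analyses and impute failure at visits with no scheduled assessment, such as SES-CD before Week 12 or Weeks 56 to 64 for Week 12 responders.

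The cost is one or two sentences. Reported rates will be slightly lower wherever data are missing.
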